## **SIGNIFICANCE**

### **CA-S. aureus burden**

Community-associated *S. aureus* infections have become a significant public health problem throughout the United States. These infections span a wide range in severity from superficial skin abscesses to invasive pyomyositis, severe necrotizing pneumonia and fatal septicemia [7-11]. Recurrent *S. aureus* SSTI are problematic and recurrence rates have been reported in up to 50% of pediatric patients [12-16]. Recurrent *S. aureus* infections requiring emergency center care is common and accounts for significant utilization of hospital resources [17]. The incidence of *S. aureus* SSTI has risen dramatically over the past decade [18], such that cellulitis and soft tissue abscesses are the most frequent primary diagnoses associated with *S. aureus*. In 2005, there were 14.2 million outpatient clinic visits for SSTI (48.1 visits/1000 in the US) compared with just 8.6 million visits (32.1 visits/1000) in 1997 [18]. Due to this substantial burden, MRSA is a top priority for the Institute of Medicine's Comparative Effectiveness Research Program [19]. The annual economic burden of MRSA infection in the United States is approximately \$14 billion [20]. At SJH and MMC in Springfield, Illinois, we have seen a significant increase in the number of pediatric ED and EC visits. In the last five years there has been an average of 1400 visits a year for SSTI, which counts for more than a fifty percent increase during this time period.

### **Determinants of CA-S. aureus infections**

Traditionally, *S. aureus* skin colonization occurs most frequently in the anterior nares, but it can also colonize the axilla, inguinal fold, rectum, and throat [5, 21]. *S. aureus* nasal colonization is a risk factor for SSTI development [22-25]. Multiple sites of *S. aureus* colonization have been found to be related to higher recurrence rates [26]. Increased rates of SSTI have been described among U.S. military personnel colonized with CA-MRSA; soldiers with CA-MRSA nasal colonization had a 10-fold greater risk of developing SSTI than soldiers colonized with Methicillin susceptible *S. aureus* (MSSA) [23]. Endogenous colonization is important in the transmission and pathogenesis of CA-MRSA infection but behavioral and environmental factors may be equally important [27].

### **Management of CA-S. aureus abscesses**

It is controversial whether abscesses requiring incision and drainage also require antibiotics [28]. The frequency of antibiotic prescription in *S. aureus* SSTI is still common as described in the literature [29]. Creech et al surveyed over 100 Pediatric Infectious Diseases Consultants and found that all of them (N=197) prescribed antibiotics; no provider reported using incision and drainage alone without antibiotic therapy [30]. Mc Neil et al reported an almost 95% rate of antibiotic prescription among children with *S. aureus* SSTI at Texas Children's Hospital [31].

In a study done by Ruhe et al, patients with SSTIs caused by MRSA benefited from antibiotic treatment. Patients with CA-MRSA SSTI who received antibiotics in addition to incision and drainage had a greater treatment success rate (infection cure) than those managed with incision and drainage alone (95% versus 87%,  $P = .001$ ) [32]. In a randomized trial by Duong et al, treatment failure rates for CA-MRSA skin abscesses were similar after incision and drainage between patients who received antibiotics and those given a placebo. However, at 10-day follow-up, new lesions formed in 26.4% of cases in the placebo group and only 12.9% of cases in the antibiotic group [12]. Schmitz et al showed a similar incidence of treatment failure in adult patients with uncomplicated abscesses receiving trimethoprim-sulfamethoxazole versus placebo (17% vs 26%,  $P = .12$ ); but at 30-day follow-up the incidence of new lesions was lower in the antibiotic group compared to the placebo group (9% vs 28%,  $P = .02$ ) [33].

### **Significance for our community**

Recurrent *S. aureus* SSTI have become a major source of morbidity in our pediatric population. Like other areas of the United States, our community has seen a dramatic increase in the incidence of skin and

soft tissue infections among previously healthy children. At SJH the number of pediatric ED visits related to SSTI increased more than fifty percent in the last 5 years, from 160 visits a year from 2008-2009 to 360 visits a year from 2013- 2014. While many of these infections are superficial, they provoke pain and anxiety for children and families, lead to subsequent scarring, and pose a significant burden through lost time from school and work. Decreasing the number of recurrent SSTI will decrease ED, EC and PCP clinic visits and will benefit our community health in general.

**INNOVATION**

Infections due to *S. aureus* are a major healthcare burden. Currently there is not an effective way to prevent *S. aureus* infection. Antibiotics are often prescribed for the treatment of CA-*S. aureus* SSTI. While incision and drainage alone may be adequate for management of uncomplicated CA-*S. aureus* skin abscesses, there is uncertainty about the requirement of systemic antibiotics. It is not known whether antibiotics are helpful in decreasing *S. aureus* colonization rates or preventing future *S. aureus* infections. Though resolution of acute abscess after drainage may be unchanged by antibiotic administration, the impact of managing *S. aureus* abscess without antibiotics on ongoing *S. aureus* colonization and recurrent infection requires further study. This study seeks to examine whether the management of initial *S. aureus* abscesses with incision and drainage in addition to antibiotic therapy is an effective means of preventing recurrent infection. The prolonged longitudinal follow-up of this study is a unique characteristic that will enable us to capture data about recurrences of infections.

**APPROACH/PRELIMINARY DATA**

**Risk factors for *S. aureus* SSTI**

MRSA colonization confers risk for SSTI: A prevalence study of *S. aureus* nasal colonization in the St. Louis pediatric population was performed by Fritz et al.; 1300 children ages birth to 18 years were enrolled. The rates of MRSA and MSSA nasal colonization were 2.5% and 25.5%, respectively [10]. To investigate the relationship between *S. aureus* nasal colonization and subsequent SSTI, the 1300 children enrolled in the above prevalence study were followed for one year, during which the overall incidence of SSTI was 13%. Baseline MRSA colonization conferred risk for subsequent SSTI (OR 4.6, 95% CI 1.8, 11.9) [10]. Another study performed by Kaplan et al showed that multiple *S. aureus* colonization sites were related with higher recurrence rates [26].

Household member with SSTI: *S. aureus* SSTI cluster in households. In a study performed by Fritz et al, SSTI in a household contact was associated with increased risk of SSTI in the index patient (Figure 1) [22].

Colonization pressure is a Risk Factor for subsequent SSTI: Colonization pressure (CP) is a measure used in healthcare settings to determine the magnitude of the microorganism reservoir. MRSA CP has been shown to predict infections in hospitals [34]. During my fellowship at Washington University under the mentorship of [name], MSCI, I participated in a study aimed to apply the concept of CP to the community setting by evaluating whether the proportion of colonized household contacts increased the prevalence of persistent colonization or the incidence of recurrent infections in index patients with baseline SSTI. We demonstrated that high MRSA CP in households was associated with persistent MRSA colonization in pediatric patients. We found a relationship between *S. aureus* household CP and a history of SSTI in household contacts in the year prior [35].

**Figure 1**  
Significant Risk Factors for Development of SSTI during a 12- Month Longitudinal Study, Univariate Analysis

| Risk Factor   | OR  | 95% CI     |
|---|-----|------------|
| MRSA nasal colonization   | 4.6 | 1.8 – 11.9 |
| Skin infection in year prior to enrollment                              | 4.2 | 1.8 – 9.7  |
| Household member with skin infection in year prior to enrollment        | 2.9 | 1.2 – 6.8  |
| Interval skin infection in a household member during one-year follow up | 6.4 | 3.4 – 12.2 |
| African-American race   | 3.1 | 1.5 – 6.4  |
| Crowded home (>2 people/bedroom)  | 4.4 | 1.1 – 18.2 |

Inclusion criteria: (1) Children 6 months to 18 years presenting with a skin abscess. (2) Positive MRSA or MSSA culture from previous or current abscess

Exclusion criteria: (1) Immunodeficiency; (2) Hospitalization within the prior 14 days; (3) Use of mupirocin, chlorhexidine or bleach water baths in the last month; (4) Systemic antibacterial therapy with anti-staphylococcal activity within the prior 14 days.

Assent will be obtained from children greater than 7 years of age. Informed consent will be obtained from the patient's parent or legal guardian. The study protocol was approved by the Southern Illinois University (SIU) Institutional Review Board (IRB). Risks for participating in the study are minimal; the only intervention that will be done is collection of body surfaces swabs.

Data Collection: At study enrollment, a detailed questionnaire will be administered to identify risk factors for *S. aureus* colonization, infection, and transmission. Clinical data will be collected as well to track clinical signs at the time of presentation (vital signs, body site of infection, size of abscess, presence of systemic symptoms, type of incision and drainage, antibiotic use, type of packing applied). In addition, colonization swabs from the nose, axilla, inguinal folds and wound isolate will be collected and transported to [name] laboratory at Washington University. Longitudinal study visits will be conducted at the SIU Pediatric Infectious Disease Clinic one month following enrollment for research purposes only by PI or by the research coordinator. At this visit, a follow-up questionnaire will be administered inquiring about new, recurrent, or relapsed infection. Colonization swabs will be obtained and transported to [name] laboratory. Also history of any household members with any recent SSTI will be asked. Follow-up phone calls will be administered at 3, 6 and 12 months after enrollment to ask about recurrent infections. If an interval infection did occur, we will collect data regarding whether the individual sought medical care (and if so, the location where medical care was sought), the date of infection, the body site of infection, the bacteria causing infection, if known, whether the individual required a drainage procedure, surgery, or hospitalization, and whether the participant received antibiotics, oral or intravenous. If the patient sought medical care, records from the hospital and/or provider's office will be obtained for verification. Again, question about any household member having an SSTI will be made. Throughout the longitudinal study, we will ask participants to contact us if they develop a SSTI. The participant will be directed to seek medical treatment from their primary healthcare provider.

Microbiology: Colonization swabs will be obtained at enrollment and at the 1 month follow-up visit by the PI or the research coordinator from the nose, axilla and inguinal folds. Four swabs will be used for each participant (1 each for both nostrils, both axillae, and both sides of the groin and the abscess site). Specimens will be collected with Copan E-swab™ Collection and Transport System to evaluate *S. aureus* colonization. This is a liquid-based multipurpose collection and transport system that maintains viability of aerobic, anaerobic and fastidious bacteria for 48 hours at room and refrigerator temperature. The research coordinator and I have successfully completed training for Shipping Infectious Materials and Biological Substances with SIU School of Medicine. Specimens will be shipped to Washington University in St. Louis, to the laboratory of [name] for microbiologic studies. If wound isolates from initial infection and a recurrence are available, they will be requested at the microbiology laboratory at SJH or MMC. After arrival, specimens will be incubated overnight in tryptic soy broth with 6.5% NaCl at 35°C. A sample of the broth will be plated to mannitol salt agar and incubated for 24-48 hours. Following confirmatory testing for *S. aureus* [37], susceptibility testing for cefoxitin (a surrogate for methicillin resistance) and 9 other antibiotics will be determined by Kirby-Bauer disk diffusion, in accordance with published guidelines [37]. Inducible clindamycin resistance will be tested [38]. All isolates will be stored in glycerol at -20°C.

Sample size: This is a pilot study to determine the feasibility of recruiting patients as described, having them return for 1 follow-up visit, and collaborating with Washington University for future

investigations. Our goal is to get preliminary data. According to available billing records (ICD-9 codes), since 2010, there has been in average 130 pediatric visits per month at SJH, MMC ED and Express Cares secondary to SSTI. Our goal is to recruit 50 patients in 12 months, which means that we will need about a 30% success rate for recruitment (**Figure 3**). A sample size estimate was performed to evaluate the power in the study. Considering an incidence of recurrent SSTI of 50% in patients who did not receive antibiotic therapy, a 60-75% percent reduction of recurrent SSTI (12-20% incidence) can be shown with 50-80% power.

[figure not shown]

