**Figure 3: Monthly Study Accrual Rates**

### Specific Aim 1:

#### Primary outcome:

To determine *overall* colonization status in children presenting with *S. aureus* abscesses who do and do not receive systemic antibiotic therapy at two time points (baseline and 1 month); a hierarchical logistic regression model will be used with colonization status as the outcome. Follow-up tests will be utilized when necessary.

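### Inclusion criterion 2 admits children whose current abscess is not S. aureus, although Aim 1 is stated for S. aureus abscesses, and no analysis separates them or names prior skin infection

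*Combined protocol and SAP*

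**What the plan says.** The eligibility criteria are listed under Approach/Preliminary Data, directly below Figure 1. Criterion 1 is "Children 6 months to 18 years presenting with a skin abscess", with no organism and no first-episode condition. Criterion 2 is "Positive MRSA or MSSA culture from previous or current abscess". None of the four exclusions concerns an earlier abscess or skin infection. The one on past systemic treatment is limited to "Systemic antibacterial therapy with anti-staphylococcal activity within the prior 14 days".

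The study question in the Innovation section is "whether the management of initial *S. aureus* abscesses with incision and drainage in addition to antibiotic therapy" prevents recurrence. The primary outcome of Specific Aim 1 is "colonization status in children presenting with *S. aureus* abscesses who do and do not receive systemic antibiotic therapy", and its first secondary outcome uses the same population.

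The Data Collection and Microbiology sections plan a swab of the abscess at enrollment, and clinical wound isolates are to be requested from the two hospital laboratories if available. Aim 2 adjusts for covariates without naming them, and Aim 1 names none. Potential limitations gives the physician's decision to prescribe as a source of bias. It then says that confounders will play no role in the colonization outcome.

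**The concern.** The population that the entry rule admits is wider than the one Aim 1 describes. A child who qualifies only on an old culture may have a current abscess with no S. aureus in it. If antibiotics act differently on colonization or recurrence in such children, the comparison answers a mixed question. If these children are spread unevenly over the treated and untreated groups, the contrast also carries a difference in case mix.

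A related gap concerns history. Figure 1 lists "Skin infection in year prior to enrollment" as a risk factor for later infection. A physician may well weigh such a history when deciding whether to prescribe. Children with that history enter by either culture route, and no model names it.

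**Working it through.** **1. The texts side by side.**

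| Place | Organism in current abscess | First episode required? |
|---|---|---|
| Inclusion criterion 1 | any | no |
| Inclusion criterion 2 | S. aureus in current *or* a previous abscess, undated | no |
| Exclusions 1 to 4 | not mentioned | no |
| Innovation | S. aureus | 'initial' |
| Aim 1, primary and first secondary outcome | S. aureus | not mentioned |

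A child with an old positive culture and a current abscess that is culture-negative, grows another organism or is not cultured meets both criteria. That child is outside the wording of Aim 1 unless S. aureus is present but undetected. A child with several earlier abscesses and a positive *current* culture also qualifies, so deleting 'previous' would not confine the study to first episodes.

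**2. Is it repaired later?** The abscess swab is collected, but no section uses its result to define eligibility or an analysis set. The enrollment questionnaire covers risk factors, and the Data Analysis Plan compares questionnaire items by group. Neither step commits the models to adjust for prior infection.

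**3. Illustration: prior infection as a confounder.** Inputs: odds ratio 4.2 (1.8 to 9.7) from Figure 1; base risks b of 12% and 20%, borrowed from the Sample size section; an assumed 60% of one group and 30% of the other with a prior abscess; no antibiotic effect.

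- Risk with prior abscess: h = o/(1 + o), where o = OR × b/(1 − b).
- b = 20%: o = 4.2 × 0.25 = 1.05, h = 51.2%. b = 12%: o = 4.2 × 0.1364 = 0.573, h = 36.4%.
- Spurious gap = (0.60 − 0.30) × (h − b).
- b = 20%: 0.30 × 31.2 = 9.4 points (38.7% v 29.4%). b = 12%: 0.30 × 24.4 = 7.3 points (26.6% v 19.3%).
- At OR 1.8 the gap is 2.3 to 3.3 points; at OR 9.7 it is 13.5 to 15.2 points.
- With equal shares the first factor is 0, and so is the gap.

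**4. Illustration: dilution by non-S. aureus abscesses.** The plan states 50 to 80% power for 50% v 12–20% recurrence with 50 children. At an assumed 25 per group, two-sided 0.05, the pooled normal formula gives 61% (50% v 20%) and 85% (50% v 12%); Fisher's exact test gives 51% and 77%. The stated range is roughly recovered and is not in dispute.

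Now let a share f of children have a non-S. aureus abscess, no antibiotic effect and 50% recurrence. The treated-group risk becomes 0.50 − (1 − f)(0.50 − p). For p = 20% and f = 20% it is 0.50 − 0.80 × 0.30 = 26%, and power falls from 61% to 41%. For p = 12.5% (a 75% reduction from 50%) and f = 20%, power falls from 84% to 61%. The documents give no value of f.

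**The case against.** This is a 50-child feasibility pilot, and broad entry is a defensible choice. Aim 2 is already to be adjusted for covariates, and the missing covariate list is a general gap, not one created by criterion 2. That stands as a reason for proportion. It does not reconcile criterion 2 with Aim 1.

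A reader might go further and infer that the entry rule contradicts a question about *first* abscesses, so that recurrent children do not belong. The documents do not support that. 'Initial' describes the study question once, in the Innovation section. The Microbiology section uses it in a sense that fits 'index', and the aims never say 'first'. A child with an earlier abscess still has an index abscess and can recur after it.

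A reader might also take the 2 to 15 points as an estimate of bias. It is not. The 60/30 split is invented, and the range does not vary it. The odds ratio is univariate and contrasts children with and without an infection in the prior year, whereas every child here has an abscess at entry and the old culture may be of any age. The base risks are the plan's figures *with* antibiotics. At 25 per group, the standard error of 38.7% v 29.4% is √(0.387 × 0.613/25 + 0.294 × 0.706/25) ≈ 13 points, larger than the gap itself.

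Finally, one might say that Aim 3 loses its isolates. Aim 3 does not require an isolate from the index abscess, and isolates from the other body sites may also be tested.

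**Conclusion.** The mismatch is real and follows from the wording alone: criterion 2 lets in children whose current abscess is not S. aureus, Aim 1 is stated for S. aureus abscesses, and no analysis separates the two. It is also established that prior skin infection, a risk factor in the protocol's own Figure 1, is not named in any model of a comparison where treatment is by physician choice. The statement under Potential limitations that confounders play no role in the colonization outcome gives no reason to leave it out.

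The size cannot be estimated. It depends on how many children enter on an old culture only, how prior infection is split between the groups, and how far the Figure 1 odds ratio carries over. The documents give none of these. The figures above show that the effect could matter, not that it does. The point merits a correction to the plan. It does not show that the results would be invalid, and it does not justify limiting the study to first abscesses.

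**What to change.** 1. Require S. aureus (MRSA or MSSA) cultured from the current (index) abscess, or keep the present entry rule and base the main Aim 1 and Aim 2 comparisons on children who meet that condition. Use the clinical culture or the enrollment abscess swab, and state beforehand whether a positive result on either is enough. Because the swab is listed among those taken to assess colonization, say that it also serves this purpose.
2. Analyze all enrolled children as a sensitivity analysis.
3. Record previous abscess or skin infection (yes/no) for every child and name it as a covariate in the Aim 1 and Aim 2 models.
4. In the Innovation section, replace 'initial' with 'index'.

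Do not limit the main analysis to first abscesses. On the illustrative 60/30 split with 25 per group, that would remove 15 + 7.5, or about 22 of the 50 children.

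Cost: no new procedure and at most one added questionnaire item. Children who qualify only on an old culture leave the main comparisons; their number is unknown. Some leave after enrollment, since culture takes overnight incubation plus 24 to 48 hours. The models are small: the Sample size figures with an assumed 25 per group imply 12.5 + 3 to 12.5 + 5, about 16 to 18 recurrences, so each added covariate costs some precision.

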### Data Analysis Plan

Data on *S. aureus* identification will be collected from Washington University School of Medicine and recorded, along with questionnaire and clinical variables, on a data collection form by the principal investigator and research coordinator and then transferred to an excel spreadsheet for statistical analysis. Statistical Package for the Social Sciences (SPSS), version 20, will be used for data analysis.

Descriptive Statistics will be computed for all study variables. Continuous variables will be described with measures of central tendency (mean, median) and dispersion (range, standard deviation). Categorical variables will be summarized as frequencies and percentages.

We will calculate the frequencies/percentages for patient demographics, clinical characteristics, baseline questionnaire, follow-up questionnaires, and *S. aureus* colonization (nose, axilla, and inguinal folds) for each group: 1) Systemic antibiotic therapy 2) No systemic antibiotic therapy. Characteristics will be compared using independent t-tests for continuous variables and Chi-squared tests of independence for categorical variables. Significance will be assumed when  $p < 0.05$  or the 95% confidence interval.

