### Potential limitations:

Recruitment success rate is estimated to be around 30% in order to collect the desired patient sample (50 patients) in a 1 year period; this is based on a prior study in which the same population was targeted [39]. We recognize the complexity of having patients come to clinic for research purposes only in follow up. SIU School of Medicine's Department of Pediatrics is providing funds to complete the study beyond the 12 month period. Patient reimbursement of a \$20 check will be given at the follow-up visit for study purposes, without any charges to medical insurance. In previous studies conducted by our team, we had had a high longitudinal retention rate when the same incentive was given [39, 40]. Specimens will be obtained by research personnel and the collection technique. The surface area swabbed and the pressure used will be standardized for all participants. We have validated the shipping procedures for specimen transport to our collaborators at Washington University. We would like to evaluate whether shipment of the swabs can be done in a timely manner and whether the length of time required for shipment impacts the ability to successfully recover microorganisms. Reaching participant for follow-up phone calls may be a challenge, especially at 6 and 12 months after study enrollment; thus, we will obtain multiple methods of contact for each participant. A source of bias that we will have is the variability in the treating physician's decision to administer antibiotics or not. Adjusting for possible confounding factors and covariates will be made but these factors will not play a role in the primary outcome which is *S. aureus* colonization.

**Conclusion:** The Research Seed Grant, RSG, is an important step in achieving my career goal of becoming an independent investigator at SIU and will offer me a tremendous opportunity to help our patient population. The goal of this project is to obtain preliminary data which will allow me to apply for future external funding to be able to recruit more patients and to show a statistical significance. Recurrent *S. aureus* SSTI have become a major source of morbidity in our pediatric population. Decreasing the number of recurrent SSTI will decrease ED and PCP clinic visits and will benefit our public health.

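### Does the 30% recruitment rate conflict with a goal of 50 patients from 130 SSTI visits a month?

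*Combined protocol and SAP*

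**What the plan says.** The Sample size paragraph describes a pilot: "This is a pilot study to determine the feasibility of recruiting patients as described". Its other purposes are to have patients return for one visit and to work with the partner laboratory. From billing records since 2010 it reports that "there has been in average 130 pediatric visits per month" for SSTI at the two hospitals' emergency departments and express care sites. It then states: "Our goal is to recruit 50 patients in 12 months, which means that we will need about a 30% success rate for recruitment", and cites Figure 3, whose caption refers to monthly accrual rates.

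Potential limitations returns to the figure: "Recruitment success rate is estimated to be around 30% in order to collect the desired patient sample (50 patients") within one year, and adds that "this is based on a prior study in which the same population was targeted".

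The inclusion criteria require a skin abscess in a child aged 6 months to 18 years and "Positive MRSA or MSSA culture from previous or current abscess". Four exclusions follow.

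The Data Collection paragraph opens at enrollment: "At study enrollment, a detailed questionnaire will be administered to identify risk factors for" colonization, infection and transmission. The Data Analysis Plan lists its descriptive summaries ("We will calculate the frequencies/percentages for patient demographics, clinical characteristics, baseline questionnaire, follow-up questionnaires, and" colonization) and gives no recruitment measure.

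**The concern.** The sentence presents the 30% as a consequence of what precedes it, and the only volume that precedes it is the visit count. Dividing the goal by that count gives about 3%, so at first sight there is a tenfold arithmetic slip. Neither place that gives the 30% says what it is a percentage of. One presents it as the rate the study needs. The other also rests it on a prior study, so a required rate and an observed rate seem to be run together.

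What would be at stake is the feasibility reading of the pilot. Recruitment is the first of its stated purposes. If the pool of suitable children is much smaller than the authors suppose, a 30% rate would not deliver 50 patients. If it is much larger, 30% would be far more than needed. The data items listed begin at enrollment, so an achieved rate among approached children could not be calculated from them.

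**Working it through.** **Inputs**
- Goal: 50 patients in 12 months (Sample size).
- Visits: 130 a month (Sample size); 1,400 a year on average (Significance, burden section); at one hospital's emergency department, 160 a year in 2008-2009 and 360 a year in 2013-2014 (Significance for our community).
- Stated rate: about 30% (Sample size; Potential limitations).
- Share of visits that yield an eligible child: not given in the text reviewed.

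**Step 1. Can the 30% be reproduced from the visit counts?** Required rate = goal / yearly visits.
- 130 x 12 = 1,560; 50 / 1,560 = 3.2%.
- 50 / 1,400 = 3.6%.
- 50 / 360 = 13.9%.
- 50 / 160 = 31.3%. This is close, but it uses the 2008-2009 count from one emergency department, which the Sample size paragraph does not use and which the plan shows had since risen to 360.

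Conversely, 30% of 1,560 visits would be 468 patients, not 50. So the 30% is not a share of the visits quoted beside it.

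**Step 2. What pool would make 30% correct?** Pool = goal / rate.
- 50 / 0.30 = 167 children a year; 167 / 12 = 14 a month.
- 167 / 1,560 = 10.7% of visits (167 / 1,400 = 11.9%).
- Reading the approximate rate as 25% to 35%: 50 / 0.25 = 200 and 50 / 0.35 = 143 a year, or about 13% to 9% of 1,560 visits.

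If 30% is of eligible children, the eligible pool must be near 167. If it is of approached children, 167 must be approached and the eligible pool can be any number at or above that. Visits are not children either, since one child can attend more than once.

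**Step 3. How much does the unstated share matter?** The shares below are assumptions; the documents give none. Eligible = share x 1,560.

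| Assumed eligible share | Eligible a year | Rate needed for 50 | Enrolled at 30% |
|---|---|---|---|
| 5% | 78 | 64% | 23 |
| 10% | 156 | 32% | 47 |
| 20% | 312 | 16% | 94 |
| 30% | 468 | 11% | 140 |

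An eligible share near 10% makes the goal and the rate agree. The inclusion criteria narrow the visits to abscesses with a positive culture, so a share well below 100% is expected. The documents do not show whether it is near 10%.

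**Step 4. Do the two statements of the 30% conflict?** The Sample size paragraph says about 30% is needed. Potential limitations says around 30% is what collecting 50 patients takes, and that earlier experience in the same population is the basis. Both hold if the study needs about 30% and the prior study supports that rate. Nothing in the documents contradicts this reading.

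**Step 5. What depends on the 30%?** The goal is a count over a fixed time. The power statement is built on a 50% recurrence incidence and a 60-75% reduction. The analyses under Aims 1 to 3 use colonization, recurrence and resistance data from enrolled children. None of them uses the recruitment rate.

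**The case for a change.** The best case for a change is that recruitment feasibility is a stated purpose, and a rate without a denominator cannot be tested. As Step 3 shows, the same 30% could yield roughly 23 or 140 children, depending on a share the text does not give. Because data collection starts at enrollment, the pilot as described could report how many children joined but not what fraction of those approached did so. It could not then compare its rate with the prior study's. A monthly count of children eligible, approached and enrolled would cost little.

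Part of this stands. The text reviewed does not name the denominator, and such a count would make the pilot more informative for planning a larger study. But the pilot's goal, 50 patients in 12 months, can be judged from the enrollment count alone. A count of children approached is a routine record that study staff can keep without a change to the design or analysis. It would add a reporting item and would not correct a result. The denominator may also be in Figure 3, so its absence from the text reviewed cannot be counted as a gap in the plan.

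**Conclusion.** No change to the plan follows. The observation is accurate as far as it goes: 30% is not a share of the 130 monthly visits (that share is 3.2%), and neither place that states it names its denominator. It does not amount to an arithmetic error, because the plan makes no claim about a share of visits and its eligibility criteria imply a narrower base. The figure is coherent if it refers to about 167 eligible or approached children a year, an implied number that the text reviewed neither gives nor contradicts. A needed rate supported by a prior-study rate is not a contradiction.

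This conclusion assumes that the 30% refers to eligible or approached children, and it allows that Figure 3 may say so. If that reading were wrong, the projected ease of recruitment would be less certain, but the goal of 50 in 12 months, the power statement and the analyses under Aims 1 to 3 would be unaffected. The point is a matter of clarity in a pilot proposal, which the investigator can settle in a phrase when reporting.
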